1.4 STUDY RATIONALE

We hypothesize that the high clinical responses noted in indolent lymphoma patients following lenalidomide and rituximab is related to the combination's ability to augment the immune response, and subsequent ADCC through alteration of immune cell subsets in the tumor and peripheral blood. Lenalidomide has been shown to activate NK cells, T cells, or both and leads to expansion of immune effector cells in-vivo in NHL and CLL models. In preclinical models, we have also shown the synergistic anti-tumor effect of combining lenalidomide with anti-CD20 molecules.

As noted above, obinutuzumab is a new, humanized anti-CD20 monoclonal antibody which binds to a unique type II epitope on the cell surface. Obinutuzumab has demonstrated increased affinity to the FCgRIIIa receptor, and may have increased ADCC when compared to rituximab. Preliminary studies also suggest the obinutuzumab is effective in patients with relapsed/refractory indolent lymphoma. (Salles et al 2011)

Combining an anti-CD20 antibody with increased affinity for the FCgRIIIa receptor with a immunomodulatory agent that increases ADCC is rational and has the potential to build upon the anti-lymphoma characteristics of both agents. Both agents are well tolerated, and the expected toxicity profile is mild.

The starting dose of lenalidomide is based upon the initial dose finding study by Wang et al which determined the maximum tolerated dose of lenalidomide with rituximab was 20mg daily in relapsed NHL. Although we do not expect

significant additional toxicity with obinutuzumab the first cohort of patients will be started at dose level 1 (10mg daily) of lenalidomide. (Wang et al 2012)

A unit dose of 1000 mg of GA101 was chosen for studies of NHL after a review of data from completed Phase I studies was undertaken. This unit dose of GA101 to be used in future studies was based on the following findings:

- No dose-limiting toxicities were observed and no maximum tolerated dose was reached in Phase I (doses from 50 mg to 2000 mg were tested).
- Clinical activity (responses) was observed at all dose levels tested.
- PK analyses suggested that a decreased variability of drug exposure related to tumor burden was achieved at doses above 800 mg given on Days 1, 8, 22 and every 3 weeks for nine doses.
- GA101 was well tolerated with a preliminary safety profile similar to that of rituximab in NHL patients (i.e., mainly Grade 1–2 toxicities, with more frequent IRRs around the time of the first infusion, decreasing with subsequent infusions).

After a comprehensive review of all safety, efficacy, and PK data obtained in Phase I studies, a total GA101 dose of 1000 mg for all infusions was chosen as the dose to be used in future Phase II and Phase III studies by the sponsor since it was the dose most likely to be well tolerated and efficacious in a majority of NHL patients regardless of their initial tumor burden.

In order to coordinate the dosing of study drugs during the first 6 months of treatment, GA101 will be given on 28-day cycles for the first six cycles in this study. On cycle 1 of therapy, the dose of GA101 will be divided over 2 days; day 1, 100mg and Day 2, 900mg. PK modeling suggests that giving additional doses of GA101 on Days 8 and 15 of Cycle 1, and then every 2 months beyond 6 months, will be needed in order to saturate target-mediated clearance achieve and maintain a steady state of drug early and as long as possible during treatment.

After the maximum tolerated dose is found, patients will be enrolled in two cohorts. Prior studies in various B cell malignancies have observed different response profiles in patients with SLL and marginal zone lymphoma compared to patients with follicular lymphoma (Fowler et al).

2. STUDY DESIGN

2.1 SCHEDULE OF STUDY ASSESSMENTS

		SCHEDULE OF STUDY ASSESSMENTS								
Procedure 8*	Screening ≤ 30days from Baseline (First day study drug administration)	Cycle 1				All Cycles *	All Cycles *	Following Cycles 3, 6, 9 ¹³ , 12 ¹³ then every 4 months during obinutuzumab maintenance* ¹⁵	Discontinuation From Study Drug	Follow-Up Phase
		Day 1	Day 8	Day 15	Day 22	Day 1	Day 14			
Record prior medications, treatments	X									
Record prior anti-cancer therapies	X									
Medical History	X	X				X				
HTLV1, HIV and Hepatitis B/C screening ¹⁰	X									
Physical examination, vital signs, weight	X	X				X			X	
ECOG performance status	X	X				X			X	
CT of the chest & abdomen / pelvis, neck, PET CT. ^{8*}	X							X	X	X ⁶
Chest x-ray	X								X	
Electrocardiogram (EKG)	X									
Bilateral bone marrow Bx, BM cytogenetics. On Follicular lymphoma histology do BM and blood PCR for Bcl-2 rearrangement. On SLL do ZAP70, CD38 staining and somatic mutation analysis on BM and tumor tissue.	X ²							X ²	X ²	

2013-0261 - Obinutuzumab Plus Lenalidomide in Low Grade Lymphoma

Register patient into Revlimid REMS® program ¹	X										
Prescribe lenalidomide via Revlimid REMS® program ¹	X					X					
obinutuzumab infusion ^{12,14}		X	X	X	X	x ¹²					
Hematology Test: hematocrit, platelet count, WBC count with differential, Absolute neutrophil count (ANC) and absolute lymphocyte count (ALC). ^{9, 11}	X	X	x	X	X	x ¹¹	X			X	
Serum chemistry: Blood chemistries should include sodium, potassium, chloride, CO ₂ , blood urea nitrogen (BUN), creatinine, glucose, aspartate aminotransferase (AST), alanine aminotransferase (ALT), total bilirubin, alkaline phosphatase, lactate dehydrogenase (LDH), calcium, ⁵	X	X	X	X	X	X	X			X	
Pregnancy test ^{3,4}	x ⁴	X	X	X	X	X	4			X	4
Tumor lesions assessment	X								X	X	x ⁶
Response assessment using IWG criteria									X	X	
Record concomitant therapies/procedures	x					X				X	
Obtain Follow-Up anti-cancer treatments										X	x ⁶
Obtain Follow-Up survival information											x ⁶

* Variations of +/- 3 days of the schedule are permitted.

** Staging CTs and BM Bx will be done up to 7 days of end of cycle

2013-0261 - Obinutuzumab Plus Lenalidomide in Low Grade Lymphoma

1. Lenalidomide must be prescribed through and in compliance with Celgene's Revlimid REMS® program. Prescriptions must be filled within 7 days.
2. Repeat BM evaluation to confirm morphologic and genetic markers of disease. Zap 70 and CD38 staining will be done if tissue is available. Repeat BM biopsy is at investigators discretion to confirm complete remission (as determined by radiographic imaging). Screening bone marrow biopsy can be obtained up to 60 days prior to study entry.
3. Pregnancy tests for females of childbearing potential. A female of childbearing potential (FCBP) is a sexually mature female who: 1) has not undergone a hysterectomy or bilateral oophorectomy; or 2) has not been naturally postmenopausal for at least 24 consecutive months (i.e., has had menses at any time in the preceding 24 consecutive months).
4. Pregnancy tests must occur within 10 – 14 days and again within 24 hours prior to prescribing lenalidomide (prescriptions must be filled within 7 days). FCBP with regular or no menstruation must have a pregnancy test weekly for the first 28 days and then every 28 days while on therapy (including breaks in therapy), at discontinuation of lenalidomide and at Day 28 post the last dose of lenalidomide. Females with irregular menstruation must have a pregnancy test weekly for the first 28 days and then every 14 days while on therapy (including breaks in therapy), at discontinuation of lenalidomide and at Day 14 and Day 28 post the last dose of lenalidomide (see Appendix: Risks of Fetal Exposure, Pregnancy Testing Guidelines and Acceptable Birth Control Methods).
5. Thyroid Stimulating Hormone (TSH) will be drawn at baseline and prior to cycles 4
6. Follow-up and tumor assessment – Patients will be evaluated every 3 months for one year, every 6 months for 1 year and then yearly with CT of neck, thorax, abdomen and pelvis and other studies as recommended by the treating physician for 1 year. Timing of imaging studies will be calculated from date of last scan. Tumor assessments, as well as timeline for tumor assessments are recommendations only. Exact timing of follow-up tumor assessments are at the discretion of the treating physician. Patients will have a minimum of imaging studies every 6 months for the first. Imaging can be done plus/-21 days of recommended time points.
7. Patient evaluation and predose labs can occur up to 3 days prior to starting each cycle. If possible, patients should be seen at least 24 hours prior to each cycle
8. If a patient is allergic to IV contrast, non-contrast PET/CT images can be used for tumor evaluation, response assessment. If patient has a history of PET negative disease, repeat PET is not required prior to study entry. If patient has full CT at specified timepoint, PET is recommended, but not required for study entry or on follow up visits.
9. If not reported on patients CBC, patient's ANC and ALC can be calculated from absolute neutrophil percent and absolute lymphocyte percent.
10. In the absence of a history of blood transfusion or intravenous drug use in the past 6 months, patients can have hepatitis B/C and HIV testing up to 8 weeks prior to study entry.
11. Hematology testing will occur on day 1 and day 14 (+/- 4 days) of cycles 2-12. If patient discontinues lenalidomide, day 14 labs are not required in cycle #2 and beyond.
12. Obinutuzumab is given on day 1, 2, 8, 15, and 22 of cycle one and on day 1 of each subsequent cycle up to 6 additional months during lenalidomide dosing. In months 12 and beyond, obinutuzumab is given every 56 days.
13. Patients can receive up to 12 cycles of lenalidomide and obinutuzumab. Restaging will occur every 3 cycles while the patient is on combination therapy, and every 112 days during obinutuzumab monotherapy (maintenance phase).
14. Obinutuzumab will be given 100mg IV on day 1, and 900mg IV on day 2 of cycle 1. Subsequent cycles will receive 1000 mg on each dose day as tolerated.
15. Cycles are 28 days long during the first 11 months of treatment (during combination and single agent dosing of obinutuzumab). The remaining cycles are 56 days. If the patient is on single agent obinutuzumab during cycle 7-12, physical exam, labs, follow up visit, ecog, vital signs, and medical history will only be done on cycles 8, 10, and 12.

2.2 OBJECTIVES

2.2.1 Primary Objectives

Part 1 (phase 1).

1. To determine the maximum tolerated dose of lenalidomide plus obinutuzumab in relapsed/refractory indolent lymphoma.

Part 2 (phase 2).

1. To evaluate the safety of lenalidomide in combination with obinutuzumab in patients with relapsed/refractory indolent lymphoma.
2. To determine the overall response rate (ORR) of the combination in patients with relapsed/refractory indolent lymphoma.

2.2.2 Secondary Objectives

1. To determine the complete response rate, time to progression (TTP), and progression free survival in patients with indolent lymphoma following treatment with obinutuzumab + lenalidomide.
2. To evaluate changes in immune effector cells and the tumor microenvironment following treatment with obinutuzumab + lenalidomide.

2.3 STUDY DESIGN

2.3.1 DESCRIPTION OF THE STUDY

This is a single-center, open label, phase I/II study in patients with refractory or relapsed indolent lymphoma. The feasibility of administrating lenalidomide in combination with obinutuzumab and the MTD of the combination will be determined in the phase I part of the study. When the MTD has been established, the efficacy of the combination will be further evaluated in the phase II part of the study in two patient cohorts simultaneously. All patients will receive a combination of daily lenalidomide for 21 days with IV obinutuzumab on day 1,2, 8, 15, and 22 of cycle one (obinutuzumab will be given 100mg IV on day 1, and 900mgIV on day 2, subsequent doses will be given over 1 day)and on day 1 of each subsequent cycle up to 6 cycles. Patients who do not progress following 6 cycles and are deriving benefit from the combination in the opinion of the treating physician can receive up to 12 cycles of lenalidomide therapy. After completing combination lenalidomide therapy, patients will then enter a “maintenance phase” and receive obinutuzumab on day 1 of each 2 month cycle for up to 2 years or a total of 30 months on treatment (combination + maintenance), whichever occurs first. The two patient cohorts are patients with follicular lymphoma (grade 1-3a) and the patients with any indolent lymphoma including follicular, marginal zone or SLL. A maximum of 72 patients (18 in phase I and 60 in phase II; the 6 patients treated at the MTD in phase I will be included in analysis

of the first group of patients treated in phase II) will be enrolled in this study on an intent-to-treat basis.

2.3.2 Phase I

The primary objective of the phase I part of the study is to determine the maximum tolerated dose (MTD) of lenalidomide when given in combination with obinutuzumab for subsequent testing in the phase II part of the trial.

There are three predefined dose levels for lenalidomide (10 mg, 15 mg, 20 mg) with a fixed dose of obinutuzumab (1000 mg) as outlined in Table 1.

Dose limiting toxicity (DLT) will be assessed during the first course of each cohort (28 days), and refers to a medically significant event which meets one of the following criteria using National Cancer Institute Common Terminology Criteria for Adverse Events (NCI CTCAE) version 4:

- Grade 3 or higher non-hematologic AE which is felt to be related to the study drug by the investigator with the exception of the following:
 - Transient grade 3 or less infusion reaction that completely resolves within 24 hours.
- Grade 4 hematologic toxicity (Platelet count is defined as <25,000 for the purposes of determining DLT).
- Grade 3 neutropenia with elevated temperature (defined as >= 101 degrees F to be confirmed on two occasions).
- Grade 3 thrombocytopenia with bleeding.
- Treatment delay of greater than 2 weeks due to treatment related toxicity.

Prior to advancing/changing dose levels a cohort summary will be completed and submitted to the Clinical Research Monitor in the IND Office.

2.3.3 Phase II

The objective for the phase II part is to further evaluate the safety and efficacy of lenalidomide when given in combination with obinutuzumab at the MTD of lenalidomide determined in phase I. The maximum number of patients that will be recruited for the phase II part is 60 with 30 for each of the two patient cohorts: the patients with follicular lymphoma (grade 1-3a) and the patients with any indolent lymphoma. The patients who are treated at the MTD in the phase I part will be counted as the first group of patients treated in phase II.

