HTLV testing is required in patients from endemic countries (Japan, countries in the Caribbean basin, South America, Central America, sub-Saharan Africa, and Melanesia)

- Pregnant or lactating
- ECOG performance status greater than 2.
- Participation in another clinical trial with drug intervention within 21 days prior to start of Cycle 1 and during the study
- Patients with SLL/CLL will be excluded during the phase I portion of the study

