4. TREATMENT PLAN

4.1 Phase I

Three dose levels of lenalidomide (10 mg, 15 mg, 20 mg) will be evaluated with a fixed dose of obinutuzumab (1000mg) as outlined in Table 1. (obinutuzumab will be given in divided doses on cycle 1; 100mg IV on day 1, and 900mg IV on day 2, subsequent doses will be given over 1 day) Up to 18 patients may participate in the Phase I component of the study, depending on the level at which toxicity is observed. Subjects will be assigned to a dose level based on the order of study entry and toxicities seen in prior patients. The dose escalation process is described below. There will be no intra-patient dose escalation. DLT will be assessed during the first course of each cohort (28 days), and refers to a medically significant event which meets criteria using National Cancer Institute Common Terminology Criteria for Adverse Events (NCI CTCAE) version 4. (see section 2.3.2)

Table 1. Dose levels to be tested in phase I portion

Dose Level	Lenalidomide Dose (days 2-22 followed by 6 days of no therapy)	Obinutuzumab dose
-1	5 mg	1000mg IV
1	10 mg	
2	15 mg	
3	20 mg	

4. 2 Phase II

Additional pts will be enrolled into two cohorts at the recommended dose level (MTD) established in Phase I up to a maximum of 30 patients each in two independently enrolling cohorts.

Cohort A: 30 patients with relapsed/refractory follicular lymphoma

Cohort B: 30 patients follicular lymphoma, marginal zone lymphoma or SLL

[figure not shown]
4. 3 Treatment Schedule

Lenalidomide capsules will be taken orally daily each day on days 2 - 22, followed by 6 days of no therapy of each 28-day cycle. Obinutuzumab will be given by intravenous infusion on day 1,,2, 8, 15, and 22 of cycle one and on day 1 of each subsequent cycle up to 6 cycles. Patients who do not progress following 6 cycles and are deriving benefit from the combination in the opinion of the treating physician can receive further cycles of combination up to 12 cycles of lenalidomide therapy. (As long as the patient does not exhibit progression, the decision of how many cycles of combination therapy beyond 6 is at the discretion of the treating team and investigator).

Extended dosing of obinutuzumab will begin after combination therapy if patients demonstrate at least stable disease on response assessment. In the extended dosing schedule, obinutuzumab will be administered every 2 months, and in the absence of progression, will be dosed for maximum of 30 months (combination + maintenance).

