5.2.1 Lenalidomide Dose and Schedule

Phase I: In the phase I portion of the study the planned dose of lenalidomide for patients with follicular lymphoma and marginal zone lymphoma (SLL patients not included in phase I portion of study) will be based upon the dose escalation table. (table 1) Patients will receive an oral dose daily on days 2 – 22 followed by 6 days rest (28 day cycle).

Table 3. Dose levels to be tested in phase I portion		
Dose Level	Lenalidomide Dose (days 2-22 followed by 6 days of no therapy)	Obinutuzumab dose
-1	5 mg	1000mg IV
1	10 mg	
2	15 mg	
3	20 mg	

Phase II: Lenalidomide will be administered orally at the maximum tolerated dose (MTD) (as defined by the Phase I portion of the study) on days 2 to 22 of a 28 day cycle in patients with follicular lymphoma and marginal zone lymphoma. Patients with a diagnosis of small lymphocytic lymphoma (SLL) will begin cycle #1 at a maximum dose of 10 mg total daily on days 2 to 22 of a 28 day cycle. This dose will be escalated by 5mg with each cycle up to the MTD if no toxicity is encountered. (see dose modification for lenalidomide table). In the absence of progression or toxicity, patients will remain on lenalidomide treatment for a total of 6-12 months/cycles.

Only one cycle of study drug will be supplied to the patient each cycle.

If a dose of lenalidomide is missed, it should be taken as soon as possible on the same day. If it is missed for the entire day, it should not be made up.

Patients who take more than the prescribed dose of lenalidomide should be instructed to seek emergency medical care if needed and contact study staff immediately. Subjects experiencing adverse events may need study treatment modifications. See Tables 6 and 7.

Supplier

Celgene Corporation will supply Revlimid® (lenalidomide) to study participants at no charge through the Revlimid REMS® program. All physicians who prescribe lenalidomide for research subjects enrolled into this trial and all research subjects enrolled into this trial must be registered in and must comply with all requirements of Celgene's Revlimid REMS® program.

Dosage form

Lenalidomide will be supplied as capsules for oral administration. The capsules are available in 2.5 mg, 5mg and 25mg capsule strengths.

Packaging

Lenalidomide will be shipped directly to the patient. Bottles will contain a sufficient number of capsules for one cycle of dosing.

Storage

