11.1 STATISTICAL/STUDY DESIGN

11.1.1 Phase I

The primary objective of the phase I part of the study is to determine the maximum tolerated dose (MTD) of lenalidomide when given in combination with obinutuzumab for subsequent testing in the phase II part of the trial. There are three predefined dose levels for lenalidomide (10 mg, 15 mg, 20 mg) with a fixed dose of obinutuzumab (1000mg) as outlined in Table 2.

Dose limiting toxicity (DLT) will be assessed during the first course of each cohort (28 days), and refers to a medically significant event which meets one of the following criteria using National Cancer Institute Common Terminology Criteria for Adverse Events (NCI CTCAE) version 4:

- Grade 3 or higher non-hematologic AE which is felt to be related to the study drug by the investigator with the exception of the following:
- Transient grade 3 or more infusion reaction that completely resolves within 24 hours.
- Grade 4 hematologic toxicity (Platelet count is defined as <25,000 for the purposes of determining DLT).
- Grade 3 neutropenia with elevated temperature (defined as >= 101 degrees F to be confirmed on two occasions).
- Grade 3 thrombocytopenia with bleeding.
- Treatment delay of greater than 2 weeks due to treatment related toxicity.

The target rate of DLT is 30%. The standard '3+3' design will be used. Applying the 3+3 design, the first cohort of 3 patients will be treated at dose level 1 and evaluated at the end of 28 days. The algorithm is as follows: (1) If 0 out of 3 patients experiences DLT, the next cohort of 3 patients will be

~~2013-0261: Obinutuzumab Plus Lenalidomide in Low Grade Lymphoma~~

treated at the next higher dose level. (2) If 1 out of 3 patients develop DLT, additional 3 patients will be treated at the same dose level. If no more DLT develops at the dose, i.e. 1 out of a total of 6 patients develops DLT, the dose escalation continues for the next cohort of 3 patients. (3) At any given dose, if greater than 1 out 3 patients or 1 out of 6 patients experience DLT, the dose level exceeds the MTD and 3 more patients will be treated at the next lower dose if there are less than 6 patients already treated at that dose. Following the above scheme, MTD is defined as the highest dose level in which 6 patients have been treated with less than 2 instances of DLT. Given 3 dose levels, it is anticipated that up to 18 eligible patients are required for the phase I part of the study.

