11.1.2 Phase II

The primary objective for the phase II part is to further evaluate the safety and efficacy of lenalidomide when given in combination with obinutuzumab at the MTD of lenalidomide determined in phase I. The maximum number of patients that will be recruited for the phase II part is 60 (include additional 54 and the 6 patients treated at the MTD in phase I) with 30 for each of the two patient cohorts: the patients with follicular lymphoma (grade 1-3a) and the patients with either follicular lymphoma, marginal zone lymphoma or SLL. The patients who are treated at the MTD in the phase I part will be included in phase II (in relevant cohort). The objective response (complete response + partial response) after 6 cycles and DLT after 1 cycle will be monitored simultaneously using the Bayesian approach of Thall, Simon, Estey (1995, 1996) as extended by Thall and Sung (1998).

Cohort A: Patients with Follicular lymphoma

Historical data on 43 patients (Witzig, 2009) with relapsed or refractory indolent non-Hodgkin's lymphoma treated with lenalidomide show an objective response (OR) rate of 23% and DLT rate of under 30%. Independence was assumed between OR and DLT. It is expected for the current trial that the two-drug combination will improve the OR rate by 20% to 43% while the DLT rate is maintained at or below 30%. A sample size of 30 patients ensures that, if the trial is not terminated early, a posterior 90% credible interval for OR rate will have width of 0.283 at most, under the assumption of a 43% of OR rate. We will claim that the regimen is worth of further investigation if the lower limit of the posterior 90% credible interval for OR rate is higher than 0.23. The probabilities of OR and DLT for the historical data are modeled by beta distributions (*Beta* (9.89, 33.11) and *Beta* (12.9, 30.1), respectively). The prior probabilities of OR and DLT for the experimental regimen are also modeled by beta distributions (*Beta* (0.46, 1.54) and *Beta* (0.6, 1.4), respectively), which have the same *means* as the corresponding beta distributions for the historical data.

Denoting the historical probabilities of objective response rate and DLT rate by $\{p(\text{OR}, \text{H}), p(\text{DLT}, \text{H})\}$, the following decision criteria will be applied:

- 1) Let E correspond to the experimental treatment, stop if

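### Early-stopping probabilities for true DLT rates of 0.40 and 0.50 are overstated in any phase II cohort that includes patients carried over from the MTD dose level, because those patients were selected for at most one DLT

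*Combined protocol and SAP*

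**What the plan says.** Section 11.1.1 sets the selection rule: "MTD is defined as the highest dose level in which 6 patients have been treated with less than 2 instances of DLT". Section 2.3.3 says that the patients "treated at the MTD in the phase I part will be counted as the first group of patients treated in phase II". Section 11.1.2 gives the count of 60 for phase II: "include additional 54 and the 6 patients treated at the MTD in phase I".

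On allocation, section 11.1.2 says only: "The patients who are treated at the MTD in the phase I part will be included in phase II (in relevant cohort". Cohort A is follicular lymphoma. Cohort B, in section 4.2, is wider: "Cohort B: 30 patients follicular lymphoma, marginal zone lymphoma or SLL". Section 3.2 adds: "Patients with SLL/CLL will be excluded during the phase I portion of the study". A follicular patient from phase I therefore fits either cohort, a marginal zone patient fits only B, and the split of the six is not fixed in advance.

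Section 11.1.2 monitors objective response after 6 cycles and DLT after 1 cycle at 10, 20 and 30 patients. The response boundaries are 1/4/7 or fewer in A and 2/6/9 or fewer in B. The DLT boundary is 7/11/15 or more in both. Each cohort has a table of early-stopping probability by true DLT rate and true response rate. Neither mentions the phase I result.

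**The concern.** The carried-over patients bring a DLT count of at most one in six, whatever the true rate. They sit among the first ten patients at the first look, where seven DLTs are needed to stop. They dilute the toxicity signal in their cohort, and the printed tables do not show this. Safety is a primary objective of phase II (section 2.2.1), and these tables are the plan's only statement of how often phase II would stop at a dose that is too toxic.

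**Working it through.** **Inputs.** Boundaries, looks and independence of response and DLT come from section 11.1.2, and the selection rule from section 11.1.1. Let k be the number of the six in a given cohort. The k values for A and B add to six, so at least one cohort has k of 3 or more.

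**Reproducing the plan's figures.** With F the probability of a futility stop and T the probability of a toxicity stop at the looks at 10 and 20,

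early stop = 1 − (1 − F)(1 − T).

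With all patients unselected, exact binomial calculation matches all 50 printed cells to four decimals. Counting the look at 30 as early does not (differences up to 0.18). Example, Cohort A, response 0.43, DLT 0.50: F = 0.0491 (the printed DLT 0.10 row, where T is 0 to four decimals) and T = 0.4346, so 1 − 0.9509 × 0.5654 = 0.462. The plan prints 0.4623.

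**Size of the selection.** P(at most 1 DLT in 6):
- DLT 0.50: 7/64 = 0.1094
- DLT 0.40: 0.6⁶ + 6 × 0.4 × 0.6⁵ = 0.2333

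Given selection, the expected DLTs among the six are 0.86 instead of 3.0 (DLT 0.50) and 0.80 instead of 2.4 (DLT 0.40).

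**Toxicity stopping after selection.** The DLT count at n = 10 is now the count in k of the six, given at most one DLT in all six, plus Binomial(10 − k, p). With k = 6 this can be done by hand at p = 0.50:
- The first look cannot trigger, since the count is at most 1 + 4 = 5. Unselected patients would trigger it with probability 176/1024 = 0.172.
- At n = 20, 11 DLTs are needed. The six hold 0 DLTs with probability 1/7 and 1 with probability 6/7. For 14 new patients, P(11 or more) = 470/16384 = 0.0287 and P(10 or more) = 1471/16384 = 0.0898.
- T = (1/7)(0.0287) + (6/7)(0.0898) = 0.081.

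| True DLT | T, unselected | k = 1 | k = 3 | k = 6 |
|---|---|---|---|---|
| 0.40 | 0.1456 | 0.1133 | 0.0608 | 0.0148 |
| 0.50 | 0.4346 | 0.3648 | 0.2347 | 0.0811 |

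**Early stopping at the target response rate** (same formula; F = 0.0491 in A and 0.0889 in B):

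| Cohort, response | True DLT | Printed | k = 1 | k = 3 | k = 6 |
|---|---|---|---|---|---|
| A, 0.43 | 0.40 | 0.1875 | 0.157 | 0.107 | 0.063 |
| A, 0.43 | 0.50 | 0.4623 | 0.396 | 0.272 | 0.126 |
| B, 0.50 | 0.40 | 0.2216 | 0.192 | 0.144 | 0.102 |
| B, 0.50 | 0.50 | 0.4848 | 0.421 | 0.303 | 0.163 |

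The k = 6 column can apply to only one cohort; the other then keeps its printed values.

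**Dependence on response rate.** The overstatement equals (1 − F) × (T unselected − T selected), so it grows as futility stopping becomes rarer. For Cohort A, DLT 0.50, k = 6, the second factor is 0.4346 − 0.0811 = 0.3535:
- response 0.13: 0.0953 × 0.3535 = 0.034
- response 0.23: 0.4580 × 0.3535 = 0.162
- response 0.43: 0.9509 × 0.3535 = 0.336
- response 0.53: 0.9918 × 0.3535 = 0.351

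The largest fall for any k is 0.022 in the DLT 0.30 rows and 0.0013 in the 0.20 rows. The 0.10 rows do not move.

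**Both phases together.** Rejected in phase I or stopped for toxicity in a given cohort = 1 − P(at most 1 of 6) × (1 − T):

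| True DLT | Unselected | k = 1 | k = 3 | k = 6 |
|---|---|---|---|---|
| 0.50 | 0.938 | 0.931 | 0.916 | 0.900 |
| 0.40 | 0.801 | 0.793 | 0.781 | 0.770 |

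The losses are about 0.75 points for k = 1, 2 points for k = 3, and 3 to 4 points for k = 6. They are upper bounds, because to become the MTD a dose must also be reached.

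**The case against.** The tables are indexed by true DLT rate and are right for independent patients at that rate, which is an ordinary way to present phase II. The documents never claim that they are conditional on phase I. The rule that creates the selection is also protective: it rejects a dose with true DLT 0.50 with probability 1 − 0.1094 = 0.89, and one with 0.40 with probability 1 − 0.2333 = 0.77. In the 0.30 row, which is the plan's acceptable limit, a lower figure means less unnecessary stopping. No boundary, sample size or decision rule is affected.

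All of this stands as a limit on the consequences. It does not make the two rows right for a cohort that receives some of the six. Phase II starts only after the selection has happened, and reading the printed figure on top of phase I protection uses the same six patients twice.

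A reader might infer three stronger things that the documents do not support. First, that the trial loses most of its protection against a toxic dose: the two-phase calculation shows at most about 4 points in a given cohort. Second, that both cohorts suffer the six-patient loss: there are only six to share. Third, that the Cohort B table is also wrong because of SLL. Section 5.2.1 says that SLL patients "will begin cycle #1 at a maximum dose of 10 mg total daily", so their cycle-1 dose differs from the others' only if the MTD is above 10 mg, and the documents give neither the SLL share nor an SLL DLT rate from which to size an effect.

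**Conclusion.** The point holds as a correction to stated operating characteristics. At DLT 0.50 and the target response rate, a cohort that receives three of the six has its early stopping overstated by 0.4623 − 0.272 = 0.190 (A) or 0.4848 − 0.303 = 0.182 (B). At least one cohort must receive three or more, and the gap widens with each further patient carried over. It is largest at or above the target response rate and small only where futility stopping dominates. The effect on the trial as a whole is modest.

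The figures assume the same true DLT rate in both phases, one DLT rate for all patients in a cohort (as the printed tables do), and allocation of the six to cohorts unrelated to whether they had a DLT. The split is not stated, so results are shown over k and no single value is claimed.

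**What to change.** In section 11.1.2:

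1. State that the printed tables assume unselected patients and apply as they stand to a cohort that receives none of the six.
2. Restate the DLT 0.40 and 0.50 rows conditional on at most one DLT among the six, for representative numbers carried over, for example 1, 3 and 6.
3. State before phase II starts which cohort follicular MTD patients enter.

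Optionally, note that the Cohort B table uses one DLT rate for all patients, which may not hold if the MTD is above 10 mg.

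Keep all boundaries and the sample size. The new values can be computed exactly. With three values of k they amount to 2 rows × 5 response rates × 3 = 30 entries per cohort, plus two statements. The one downside is that the stopping probabilities in those rows become less favourable.
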